### **3.8 Data Safety and Monitoring Board**

A Data Safety Monitoring Board will review safety data periodically in collaboration with the Sponsor to ensure subject safety. A separate DSMB charter will establish the rules, meeting frequency, and scope of responsibilities of the DSMB.

## 4 ELIGIBILITY CRITERIA

### 4.1 Inclusion Criteria

1. Age  $\geq$  18 years.
2. Subject has been informed of the investigational nature of this study and has given written informed consent in accordance with institutional, local, and national guidelines.
3. Receiving HD or PD for ESRD for a minimum of 2 weeks and a maximum of 4 months, prior to randomization.
4. Hemodialysis access consisting of an arteriovenous (AV) fistula, AV graft, or tunneled (permanent) catheter; or PD catheter in use.
5. Mean of the two most recent predialysis Hb values during the Screening Period, obtained at least 2 days apart, must be  $\leq$  10.0 g/dL, with a difference of  $\leq$  1.3 g/dL between the highest and the lowest values. The last Hb value must be drawn within 10 days prior to randomization.
6. Ferritin  $\geq$  100 ng/mL ( $\geq$  220 pmol/L); subjects with ferritin level  $<$  100 ng/mL ( $<$  220 pmol/L) during screening, qualify after receiving iron supplement (per local standard of care), without the need to retest ferritin prior to randomization.
7. Transferrin saturation  $\geq$  20%; subjects with TSAT level  $<$  20% during screening, qualify after receiving iron supplement (per local standard of care), without the need to retest TSAT prior to randomization.
8. Serum folate level, performed within 8 weeks prior to randomization  $\geq$  lower limit of normal (LLN); subjects with serum folate level  $<$  LLN during screening, qualify after receiving folate supplement (per local standard of care), without the need to retest folate prior to randomization.
9. Serum vitamin B12 level, performed within 8 weeks prior to randomization  $\geq$  LLN; subjects with vitamin B12 level  $<$  LLN during screening, qualify after receiving B12 supplement (per local standard of care), without the need to retest B12 prior to randomization.
10. Alanine aminotransferase (ALT) or aspartate aminotransferase (AST)  $\leq$  3 x upper limit of normal (ULN), and total bilirubin (Tbili)  $\leq$  1.5 x ULN.
11. Body weight up to 160 kg (HD subjects: dry weight).

### 4.2 Exclusion Criteria

1. Total duration of prior effective ESA use must be  $\leq$  3 weeks within the preceding 12 weeks at the time informed consent is obtained.

**Specific dosing guidance, depending on the type of ESAs, injected IV or SC within 12 weeks prior to start of screening are as follows:**

Short-acting ESAs (EPO-alfa or equivalents)

- IV: Up to 9 doses; last EPO dose must be  $\geq$  2 days prior to start of screening

- SC: Up to 3 doses; last EPO dose must be  $\geq$ 1 week (7 days) prior to start of screening

#### Darbepoetin

- IV: Up to 3 doses; last darbepoetin dose must be  $\geq$ 1 week (7 days) prior to start of screening
- SC: Up to 2 doses; last darbepoetin dose must be  $\geq$ 2 weeks (14 days) prior to start of screening

#### Continuous erythropoietin receptor activator (CERA) IV and SC

- IV or SC: Up to 2 doses; last CERA dose must be  $\geq$ 2 weeks (14 days) prior to start of screening

2. Intravenous iron: there is no restriction regarding IV iron use during screening, provided it is administered in accordance with local standard of care.
3. Red blood cell transfusion within 4 weeks prior to randomization.
4. Active, clinically significant infection that could be manifested by white blood cell (WBC) count  $>$  ULN, and/or fever, in conjunction with clinical signs or symptoms of infection at the time of randomization.
5. History of chronic liver disease (eg, chronic infectious hepatitis, chronic auto-immune liver disease, cirrhosis, or fibrosis of the liver).
6. New York Heart Association Class III or IV congestive heart failure at screening.
7. Myocardial infarction, acute coronary syndrome, stroke, seizure, or a thromboembolic event within a major vessel (excluding vascular dialysis access) (eg, deep vein thrombosis or pulmonary embolism) within 12 weeks prior to randomization.
8. Uncontrolled hypertension, in the opinion of the Investigator, (eg, that requires a change in anti-hypertensive medication) within 2 weeks prior to randomization.
9. Renal imaging performed within 12 weeks prior to randomization indicative of a diagnosis or suspicion (eg, complex kidney cyst of Bosniak Category 2 or higher) of renal cell carcinoma.
10. History of malignancy, except for the following: cancers determined to be cured or in remission for  $\geq$  5 years, curatively resected basal cell or squamous cell skin cancers, cervical cancer in situ, or resected colonic polyps.
11. Positive for any of the following: human immunodeficiency virus (HIV); hepatitis B surface antigen (HBsAg); or anti-hepatitis C virus antibody (anti-HCV Ab).
12. Chronic inflammatory disease that could impact erythropoiesis (eg, systemic lupus erythematosus, rheumatoid arthritis, celiac disease) even if it is currently in remission.
13. Known, untreated proliferative diabetic retinopathy, diabetic macular edema, macular degeneration, or retinal vein occlusion (subjects who are already blind for the above reasons qualify to participate).

14. Known history of myelodysplastic syndrome or multiple myeloma.
15. Known hereditary hematologic disease such as thalassemia or sickle cell anemia, pure red cell aplasia, or other known causes for anemia other than CKD.
16. Known hemosiderosis, hemochromatosis, coagulation disorder, or a hypercoagulable condition.
17. Organ transplant: subjects with any of the following:
  - a. Experienced rejection of a transplanted organ within 6 months of transplantation
  - b. Currently on high doses of immunosuppressive therapy (per discretion of the Investigator)
  - c. Scheduled for organ transplantation. Note: being on a waiting list for kidney transplant is not exclusionary
18. Anticipated elective surgery, except for vascular access surgery or dialysis catheter placement, that is expected to lead to significant blood loss, or anticipated elective coronary revascularization.
19. Active or chronic gastrointestinal bleeding.
20. Any prior treatment with roxadustat or a HIF-PHI.
21. Use of iron-chelating agents within 4 weeks prior to randomization.
22. Known hypersensitivity reaction to any ESA.
23. Use of an investigational drug or treatment, participation in an investigational study, or presence of an expected carryover effect of an investigational treatment, within 4 weeks prior to randomization.
24. Anticipated use of dapsone or androgens at any dose amount or chronic use of acetaminophen or paracetamol > 2.0 g/day during the study.
25. History of alcohol or drug abuse within 6 months prior to randomization.
26. Females of childbearing potential, unless using contraception as detailed in the protocol; male subjects with sexual partners of childbearing potential who are not on birth control unless the male subject agrees to use contraception.
27. Pregnant or breastfeeding females.
28. Any medical condition that, in the opinion of the Investigator, may pose a safety risk to a subject in this study, may confound efficacy or safety assessment, or may interfere with study participation.

Subjects who fail to meet the above eligibility criteria should not be randomized or receive study medication. If Day 1 lab values (collected prior to administration of study medication) are found to be of significant safety risk, in the opinion of the Investigator or Medical Monitor, the subject may be discontinued from the study.

## 5 INVESTIGATIONAL PRODUCT

### 5.1 Formulation

Roxadustat is supplied by FibroGen, Inc. as red coated, oval tablets for oral administration, in strengths of 20 mg, 50 mg and 100 mg. The excipients include lactose monohydrate, microcrystalline cellulose, povidone, croscarmellose sodium, magnesium stearate, and colorant Red Opadry 2. All ingredients used for manufacture of roxadustat comply with US and European Union compendial or regulatory standards. Strengths are different in size, and debossing reflects the strength (ie, 20, 50 or 100 mg). Due to the light-sensitive nature of roxadustat and to minimize exposure of the active pharmaceutical ingredient to light, tablets should remain in the original packaging for as long as possible and be administered as intact tablets only.

### 5.2 Storage

Roxadustat tablets should be protected from light, and stored at 15° to 30°C (59°–86°F).

Epoetin alfa should be stored according to the USPI or SmPC.

All study drug (roxadustat and epoetin alfa) should be stored in a securely locked area to which access is limited to appropriately qualified and authorized study personnel.

Handling and disposition of unused study drug is described in the site Drug Accountability Binder.

### 5.3 Administration

#### 5.3.1 Roxadustat

Roxadustat should be dispensed to subjects with instructions for self-administration of the tablets on each dosing day, according to the dosing schedule below. The tablets are to be swallowed whole with room-temperature drinking water. Dosing should occur at approximately the same time of day.

Study drug doses taken TIW must be administered at least 2 days apart, and no more than 4 days apart. Dosing days should remain consistent throughout the study. If a subject requires < 20 mg TIW (ie, < 60 mg per week) to maintain Hb levels in the Maintenance Phase, the dosing frequency should be reduced in a step-wise fashion eg, TIW to BIW, BIW to QW, QW to Q-2 Week etc.

#### 5.3.2 Active Control-Epoetin Alfa

##### 5.3.2.1 Hemodialysis Subjects

Epoetin alfa will be administered IV TIW according to the Package Insert or SmPC by appropriately trained personnel. In subjects requiring ultra-low dose of EPO (eg,  $\leq 1000$  IU/week), the frequency of administration may be adjusted by the PI per local standard of care. For countries provided with prefilled syringes, the initial epoetin alfa dose and dose adjustments should be approximated to the closest calculated total weekly dose.

##### 5.3.2.2 Home-hemodialysis and Peritoneal Dialysis Subjects

Epoetin alfa will be administered according to the Package Insert, or SmPC or local standard of care by appropriately trained personnel including subject or caregiver. For countries provided

with prefilled syringes, the initial epoetin alfa dose and dose adjustments should be approximated to the closest calculated total weekly dose.

#### **5.4 Overdose, Emergency Procedures and Management of Overdose**

The maximum tolerated dose of roxadustat has not been established in humans. For the purpose of this study, the maximum allowed roxadustat dose is set at 3.0 mg/kg/dose or 3.5 mg/kg/dose from the original protocol (based on dry weight in subjects on HD and normal weight in subjects on HHD and PD) or 400 mg per administration, whichever is lower. Any dosing exceeding the maximum allowed roxadustat dose should be reported within 24 hours.

The Medical Monitor should be contacted as soon as possible. Symptoms associated with overdosing, if any, will be reported as AEs. An overdose without associated symptoms is not an AE and will be recorded on the dosing case report form (CRF) only.

In the event of suspected roxadustat overdose, the subject should receive supportive care and monitoring. The Sponsor's Medical Monitor should be contacted as applicable.

In the event of suspected epoetin alfa overdose, refer to the epoetin alfa USPI of SmPC.

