### 3.5.3 Dose Adjustment for Roxadustat

Dose adjustments will occur in two separate study dosing phases: the Correction Phase and the Maintenance Phase. Each of these phases will follow unique adjustment rules according to [Appendix 2](#).

All subjects will be dosed orally TIW during the Treatment period. The maximum roxadustat dose is 3.0 mg/kg per dose or 400 mg (whichever is lower).

All dose adjustments as well as assessments of excessive hematopoiesis are based on Hb values using a point-of-care device, such as HemoCue® or CritLine®. In the event that the central lab Hb value of the site visit is significantly different and the dose adjustment decision based on the HemoCue® / CritLine® value is being re-considered, the Medical Monitor should be contacted, if possible.

The determination of Hb response and transition from the Correction to the Maintenance Phase of the study is based on the central laboratory Hb value.

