### 3.5.3.2 Maintenance Phase of Dosing for Roxadustat

- The aim of the Maintenance Phase is to maintain Hb levels after the initial correction by using the dose adjustment algorithm in [Appendix 2](#).

Note: Given the complexity in roxadustat dose adjustments, and the need to take into account the various clinical parameters in roxadustat dose titration, one would not consider it a protocol deviation when study subjects are dosed based on their clinical circumstances, whether or not it is concordant with the roxadustat dose adjustment guidelines unless it was related to "excessive hematopoiesis" (eg, Hb  $\geq 13$  g/dL, requiring a dose hold) or "Overdose" (prescribed  $>3.0$  mg/kg per dose or 400 mg per dose whichever is lower).

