2. Hb reaches or exceeds 13 g/dL: hold dosing, check Hb weekly. Resume dosing when Hb < 12.0 g/dL (for US subjects central lab Hb value preferred), at a dose that is reduced by two dose steps.

For subjects on prolonged dose-hold, with stable (not dropping) Hb, PI may use discretion to schedule less frequent visits. Anytime Hb is assessed via HemoCue®/CritLine®/local lab, a central lab Hb should be obtained as well.

Given the complexity in roxadustat dose adjustments, and the need to take into account the various clinical parameters in roxadustat dose titration, one would not consider it a protocol deviation when study subjects are dosed based on their clinical circumstances, whether or not it is concordant with the roxadustat dose adjustment guidelines unless it was related to "excessive hematopoiesis" (eg., Hb ≥ 13 g/dL, requiring a dose hold)) or "Overdose" (prescribed >3.0 mg/kg per dose or 400 mg per dose whichever is lower)

CORRECTION PHASE			MAINTENANCE PHASE			
Change in Hb from 4 weeks earlier (g/dL)	Hb < 11 g/dL (central lab)*	Hb ≥ 13.0 g/dL	Hb < 10.5 g/dL	Hb 10.5 to 11.9 g/dL	Hb 12.0 to 12.9 g/dL	Hb ≥ 13.0 g/dL
< -1.0	↑		↑	↑	No change	
-1.0 to 1.0	↑	Hold, then resume dosing when:  Hb < 12 g/dL, at a dose that is reduced by two dose steps Subjects are to return weekly to monitor Hb until dosing can be resumed**	↑	No change	↓	Hold, then resume dosing when:  Hb < 12 g/dL, at a dose that is reduced by two dose steps Subjects are to return weekly to monitor Hb until dosing can be resumed**
> 1.0	No change		No change	↓	↓	
Dose Increases and Reductions:			Dose Adjustment for Excessive Hematopoiesis:			

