
Dose increases (↑) and reductions (↓) are preset to dose steps. The dose steps are as follows: 20, 40, 50, 70, 100, 150, 200, 250, 300, and 400 mg.
 
Example: A dose increase at a dose of 70 mg results in 100 mg as the new dose. A dose reduction at a dose of 150 mg results in 100 mg as the new dose.
 
Note: Maximum dose capped at 3.0 mg/kg per dose or 400 mg, whichever is lower.
 
*Transition from Correction to Maintenance Phase will occur once the central laboratory Hb value is ≥ 11 g/dL and ≥ 1 g/dL from baseline
				
At any time during the Treatment Period if Hb increases by >2.0 g/dL within 4 weeks, the dose should be reduced by one dose step.
 
** For subjects on prolonged dose-hold, with stable (not dropping) Hb, PI may use discretion to schedule less frequent visits. Anytime Hb is assessed via HemoCue®/CritLine®/local labs, a central lab Hb should be obtained as well
		

Abbreviations:      ↑ = increase; ↓ = decrease; Hb = hemoglobin.

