3 STUDY DESIGN

This is a Phase 3, multicenter, randomized, open-label, and active-controlled study to evaluate the efficacy and safety of roxadustat in incident dialysis subjects with anemia.

A total of up to 1,200 subjects are planned to be randomized to receive roxadustat or epoetin alfa (active control) in a 1:1 ratio, respectively.

Randomization stratification factors include geographical region (US vs. Ex-US), screening Hb values (≤ 8 g/dL vs. >8 g/dL), and cardiovascular/cerebrovascular/thromboembolic medical history (yes vs. no).

In addition, the change of protocol were incorporated via amendments on 20 Oct 2014, 24 Nov 2015, 12 Aug 2016, and current one on 20 September 2017.

Subjects randomized to roxadustat will have doses administered thrice weekly (TIW) throughout the Treatment Period using an initial tiered, weight-based, dosing scheme (see Table 1 below), followed by dose titration every 4 weeks.

Table 1. Initial Study Drug Dosing

Study Drug (Dose Frequency)	Low Weight/Dose	Median Weight/Dose	High Weight/Dose
Roxadustat (TIW) – Original Protocol	45 to 60 kg/70 mg	>60 to 90 kg/100 mg	>90 to 160 kg/150 mg
Roxadustat (TIW) – Amended Protocol	≤ 70 kg/70 mg		>70 to 160 kg/100 mg
Epoetin alfa HD (TIW)	IV dosing according to epoetin alfa USPI or SmPC		
Epoetin alfa PD (TIW)	Epoetin alfa should be administered according to epoetin alfa USPI or SmPC or local standard care.		
	Abbreviations: HD = hemodialysis; IV = intravenous; PD = peritoneal dialysis; SmPC = summary of product characteristics; TIW = three times a week; USPI = United States Package Insert; wt = weight. Note: Weight in HD subjects = subject's dry weight.		

The study periods are as follows:

- Screening Period: Up to 6 weeks
- Treatment Period: Treatment duration is variable for individual subjects with maximum treatment duration of up to approximately 3 years after the last subject is randomized. The minimum treatment duration may be less than 52 weeks.
- Post-Treatment Follow-Up Period: 4 weeks

Dose Adjustments

Roxadustat arm

Dose adjustments will occur in two separate study dosing phases: the Correction Phase and the Maintenance Phase. Each of these phases will follow unique dose adjustment rules according to Appendix 2 in the amended protocol of 20 October 2014. All subjects in the roxadustat arm will be dosed orally TIW during the Treatment Period. The maximum roxadustat dose is 3.0 mg/kg per dose or 400 mg, whichever is lower.

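### Protocol Section 5.4 names two mg/kg ceilings for roxadustat, while the other dosing passages and the overdose definition use 3.0 mg/kg only

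*Protocol*

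**What the plan says.** Section 5.4 of the protocol states that "the maximum allowed roxadustat dose is set at 3.0 mg/kg/dose or 3.5 mg/kg/dose from the original protocol". A bracket on which body weight to use follows, and the sentence ends "or 400 mg per administration, whichever is lower". The next sentence attaches a duty to that ceiling: "Any dosing exceeding the maximum allowed roxadustat dose should be reported within 24 hours".

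The other passages that set a maximum give one mg/kg figure. The table note in Appendix 2 reads "Maximum dose capped at 3.0 mg/kg per dose or 400 mg, whichever is lower". SAP Section 3 reads "The maximum roxadustat dose is 3.0 mg/kg per dose or 400 mg, whichever is lower". The Synopsis, Section 3.5.3 and the text of Appendix 2 say the same. None of them makes an exception for subjects who entered under an earlier version of the protocol.

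Two passages go beyond setting a maximum. The note in Section 3.5.3.2, repeated in Appendix 2, says that departing from the roxadustat dosing algorithm is generally not a protocol deviation. It excepts excessive hematopoiesis and overdose, and defines overdose as a prescribed dose above 3.0 "mg/kg per dose or 400 mg per dose whichever is lower". Section 9.2.5 lists overdose among the special situations that require reporting, but gives no threshold.

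**The concern.** A site deciding whether a dose must be reported within 24 hours will turn to Section 5.4, and that is the one place with two ceilings. The words tying 3.5 mg/kg to the original protocol suggest either an allowance for subjects enrolled under that version or text left over from it. Section 5.4 does not say which.

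If 3.5 mg/kg applies to anyone, a dose above 3.0 and up to 3.5 mg/kg does not exceed the Section 5.4 maximum and does not trigger its 24-hour rule. Under Section 3.5.3.2 and Appendix 2 the same dose is an overdose and is not exempt from deviation status. Section 9.2.5 then lists overdose as reportable. Two sites could classify the same prescription differently, each with protocol text to support it. What is at stake is consistent notification of high doses and a consistent count of dosing deviations.

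**Working it through.** The plan has no sample size, power or error rate on this point to reproduce. The check has two parts: whether the passages can be read together, and whether the protocol's own dose steps can land between the two ceilings.

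**Possible readings of Section 5.4**

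| Reading | Effective mg/kg ceiling | Agrees with the other passages? |
|---|---|---|
| The lowest-figure clause covers all three figures | 3.0 for everyone | Yes, but 3.5 then has no function |
| 3.5 applies to subjects from the original protocol, 3.0 to the rest | 3.5 or 3.0 by version | No: no other passage has the exception, and those subjects' doses above 3.0 mg/kg are overdoses under Section 3.5.3.2 and Appendix 2 |
| Either figure may be used for anyone | 3.5 in effect | No |

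Only the first reading removes the conflict, and it does so by leaving one of the stated figures without meaning.

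**Inputs**

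- Ceilings: k = 3.0 and k = 3.5 mg/kg, with a 400 mg cap (Section 5.4).
- Dose steps: 20, 40, 50, 70, 100, 150, 200, 250, 300 and 400 mg (Appendix 2).
- Body weight: up to 160 kg (inclusion criterion 11).

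**Ceiling in mg.** For weight w, the ceiling is min(k × w, 400). The 400 mg cap takes over at 400 / 3.0 = 133.3 kg for the lower ceiling and at 400 / 3.5 = 114.3 kg for the higher one. The two ceilings differ at every weight below 133.3 kg and are both 400 mg from there to 160 kg.

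**Steps between the ceilings.** A step of d mg is above 3.0 and at or below 3.5 mg/kg when d / 3.5 ≤ w < d / 3.0.

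| Step (mg) | From d / 3.5 (kg) | To below d / 3.0 (kg) |
|---|---|---|
| 150 | 42.9 | 50.0 |
| 200 | 57.1 | 66.7 |
| 250 | 71.4 | 83.3 |
| 300 | 85.7 | 100.0 |
| 400 | 114.3 | 133.3 |

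For steps of 100 mg and below, the band ends at or under 100 / 3.0 = 33.3 kg, so they are left out.

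**Examples**

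- At 80 kg the ceilings are 3.0 × 80 = 240 mg and 3.5 × 80 = 280 mg. The 250 mg step (250 / 80 = 3.125 mg/kg) lies between them. The highest step within the ceiling is 200 mg under one and 250 mg under the other.
- At 75 kg the ceilings are 225 mg and 262.5 mg, and 250 mg is 250 / 75 = 3.33 mg/kg, again between them.
- At 85 kg the ceilings are 255 mg and 297.5 mg. The highest step is 250 mg under both, so no listed step is affected.
- At 134 kg the cap of 400 mg governs both.

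**The case against.** The best defence is that Section 5.4 ties the higher figure to the original protocol, so it does not simply offer a choice of two limits. The SAP also distinguishes protocol versions: Table 1 gives separate original and amended starting doses, and SAP Section 5.4 lists protocol version among the analysis factors. In addition, if the closing clause about the lowest figure covers all three numbers, Section 5.4 reduces to 3.0 mg/kg or 400 mg, as elsewhere. Both points stand as far as they go. They make Section 5.4 ambiguous rather than plainly permissive. They do not settle who is covered, and SAP Section 3 states a single 3.0 mg/kg maximum directly after separating the two versions.

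Practical reach may also be small. The passages that govern prescribing all cap at 3.0 mg/kg, so a site following Appendix 2 would not prescribe 250 mg at 80 kg. Section 1.4.2.2 reports that maintenance doses in a Phase 2 dialysis study were mostly 0.7 to 2.0 mg/kg, with occasional subjects needing up to 3.0 mg/kg. Symptoms of an overdose are reported as adverse events in any case, and serious events go to the sponsor within 24 hours under Section 9.3.5. The reporting gap therefore mainly concerns doses between the ceilings that cause no serious event.

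Four stronger readings are tempting, and the documents do not support them:

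- *The protocol openly permits 3.5 mg/kg for everyone.* The reference to the original protocol and the lowest-figure clause both speak against this.
- *Every passage makes a dose above 3.0 mg/kg an overdose and a deviation.* Section 3.5.3 and SAP Section 3 only set a maximum. The overdose and deviation link is in Section 3.5.3.2 and Appendix 2, and the reporting link outside Section 5.4 comes from Section 9.2.5.
- *The Per Protocol Set is affected.* SAP Table 2 does not list overdose or a mg/kg ceiling. Its list is open and one criterion is judged case by case, so an effect is possible but not shown.
- *Sites have in fact reported inconsistently.* Nothing in the documents shows this. The text only allows it.

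**Conclusion.** The inconsistency is real and lies in the current text. Section 5.4 can be read to place a dose above 3.0 and up to 3.5 mg/kg within the maximum and outside its 24-hour rule. Section 3.5.3.2 and Appendix 2 make that dose an overdose that is not exempt from deviation status.

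The conflict is limited to subjects below about 133 kg. For the listed dose steps it arises in the five weight bands shown, which take in much of the range from about 43 to 133 kg. How many subjects would be prescribed such a dose cannot be worked out from the documents. The conclusion assumes that the 3.5 mg/kg figure is meant to have some effect; if it is a leftover, the fault is redundant wording in a safety threshold. Either way it should be corrected, because the sentence decides when a report is due. No position is taken on which limit is right.

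**What to change.** Reconcile Section 5.4 with the Synopsis, Sections 3.5.3 and 3.5.3.2, Appendix 2 (text, overdose note and table note) and SAP Section 3. The maximum dose, the 24-hour reporting trigger and the overdose and deviation definition should use the same threshold. If a different ceiling is meant for subjects under an earlier protocol version, state that exception and exactly whom it covers in each of these places. If it is not, remove the ambiguity from Section 5.4. Section 9.2.5 could then refer to the agreed definition.

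The cost is wording in the protocol and one line in the SAP, with a clarification to sites. Sample size, endpoints and analysis methods are unchanged.
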